Version date: 6/21/2022

Study Title: The Adaption of the GameSquad Exergaming Intervention for Young Adults with Down Syndrome: A Pilot Feasibility Study

I. Purpose, Background and Rationale

A. Aim and Hypotheses

1. The 5-year transitional period between adolescence and young adulthood is known to be a period of increased risk for the development of obesity, unhealthy diet, and low physical activity (PA) levels¹. The limited research in individuals with Down syndrome (DS), a population with a high prevalence of obesity and higher rates of functional decline, mobility restrictions, frailty, musculoskeletal problems, osteoporosis, and sleep problems, suggests this transition period impacts individuals with DS in a similar manner¹. Increased moderate-to-vigorous physical activity (MVPA) is associated with improved physical and cognitive function². However, participation in MVPA among adults with intellectual disabilities (ID), including DS is extremely low when compared to typical functioning adults³. Adults with DS face unique barriers to participation in MVPA^{4,5}. Exergames, which integrate MVPA into video game play are an affordable, accessible, home-based exercise program which has shown effectiveness for increasing MVPA and improving both physical and cognitive function in typically developed populations⁶. An exergaming intervention with individual health coaching called GameSquad has been shown to be effective in improving MVPA and cardiometabolic parameters in children with overweight/obesity and adolescents with neurodevelopmental and psychiatric diagnoses^{7,8}. We propose a project to adapt/evaluate the GameSquad intervention for use in adults with DS (GameSquad-DS). We will conduct a 12-wk. single arm pilot trial in 20 young adults with DS to assess the acceptability, appropriateness, and feasibility of the intervention and calculate effect sizes for change MVPA, physical function, muscular strength, physical activity enjoyment, and self-efficacy. Successful completion of this project represents an initial step in achieving our goal of developing effective interventions to increase MVPA and promote healthy aging in adults with DS.
2. Primary aim: To assess the acceptability, appropriateness, and feasibility of the intervention using various quantitative alongside qualitative data. Specifically, we will assess mins/wk of Ring-Fit Adventure™ played, attendance at virtual health coaching sessions, semi-structured interviews, participant retention, and intervention safety measured as number of adverse events.

Secondary aim: To calculate effect sizes for change across 12-wks. in MVPA, physical function, muscular strength, physical activity enjoyment, and self-efficacy. We hypothesize increases in MVPA, physical function, muscular strength, physical activity enjoyment, and self-efficacy.

Secondary aim: To determine energy expenditure of a session of Ring-Fit Adventure™ among adults with DS. We hypothesize energy expenditure akin to moderate physical activities.

B. Background and Significance

1. Study Significance: Down syndrome (DS) or trisomy 21 is the most common chromosomal abnormality associated with an intellectual disability (ID). The current incidence of DS is 1 in every 650 live births which is ~30% higher than in 1979, largely due to women conceiving after age 35. Additionally, life expectancy for people with DS has increased dramatically over the past 60 years due to advancements in disease knowledge, medical care, and caregiving services⁹. With this increase in DS prevalence through improved life expectancy, it is critical to address ways to support healthy living throughout their lifespan. Adults with DS have a higher prevalence of obesity¹⁰ and obesity associated health conditions including sleep apnea and type 2 diabetes¹¹ compared to adults without DS. Additionally, adults with DS face premature aging¹², higher rates and earlier onset of Alzheimer's disease (AD)¹³, functional decline, mobility restrictions, frailty, musculoskeletal problems, osteoporosis, and sleep problems when compared with typically developed adults¹⁴. These increased rates of chronic disease and functional decline are associated with reduced quality of life, and increased burden on families, care providers, and disability services. Chronic disease also contributes to absenteeism from disability employment, premature withdrawal from the workforce, and increased health care utilization¹⁵.
2. We recently asked 10 adults with DS who visited our lab to complete assessments for an on-going trial (TL1TR002368) to play the introductory game on Ring-Fit Adventure™ for ~15 minutes while wearing a portable accelerometer on a belt at waist. Approximately 7 minutes provided instructions on how to use the game and ~8 minutes predominately light physical activity active play. Participants enjoyed playing the game and felt the game would be feasible and safe for home use. The accelerometer data indicated ~5 minutes of light and ~3 minutes of MVPA, which appeared reasonable based on the types of activities included in the game. Thus, based on these preliminary results we propose to adapt the GameSquad intervention using the Ring-Fit Adventure™ as our exergaming platform for use in transition age young adults with DS (18-25 yrs.)
3. Literature Review: A 24-wk. randomized trial in 46 children with overweight/obesity using a home-based intervention which incorporates exergaming (Xbox Kinect) with individual health coaching called GameSquad demonstrated reduced BMI-z score ($p=0.016$) and improved systolic and diastolic blood pressure, total and low-density lipoprotein cholesterol, and MVPA relative to wait-list control (all $p < 0.05$)⁷. Members of our study team recently conduct a 10-wk pilot trial of the game GameSquad intervention (3 exergaming sessions/wk., plus 6 health coaching sessions) adapted for use with adolescents with neurodevelopmental and psychiatric diagnoses ($n=23$, age ~ 15 yrs.)⁸. Participants reported an average of ~82 min/wk. of exergaming and completed 83% of the scheduled health coaching sessions. Unfortunately, both the original and Adaptive GameSquad interventions used the Xbox Kinect gaming system which was discontinued in 2017. Nintendo Ring-Fit Adventure™ is a novel, and currently popular exergame that uses both a resistance ring and body weight to perform numerous upper and lower body cardiovascular and resistance exercises. In contrast to other exergames, participants incorporate exercise to complete an adventure narrative guided by Ring-Fit Adventure™ characters. The narratives provide ~60 hours of unique activity which increases in both intensity and difficulty as participants progress through the game. Participant exercise is guided by both written instructions and visual demonstrations via an in-game avatar. Feedback regarding proper exercise form is provided by controllers/ accelerometers

imbedded in the game ring. Formative work by [name] found that Ring-Fit Adventure™ was the most enjoyable and user-friendly of the 4 evaluated exergames.

C. Rationale

1. The original GameSquad among children and the adapted GameSquad among adolescents with neurodevelopmental and psychiatric diagnoses have both demonstrated strong potential. We now want to further adapt the GameSquad concept for young adults with Down Syndrome.
2. Successful completion of this project represents an initial step in achieving our goal of developing effective interventions to increase MVPA and promote healthy aging in adults with DS.

II. Research Plan and Design

A. Study Objectives: Primary aim: To assess the acceptability, appropriateness, and feasibility of the intervention using quantitative data alongside qualitative data. Specifically, we will assess mins/wk of Ring-Fit Adventure™ played, attendance at virtual health coaching sessions, semi-structured interviews, participant retention, and intervention safety measured as number of adverse events.

B. Secondary aims: To calculate effect sizes for change across 12-wks. in MVPA, physical function, muscular strength, physical activity enjoyment, and self-efficacy.

C. Exploratory aim: To determine energy expenditure of a session of Ring-Fit Adventure™ among adults with DS.

D. Study Type and Design: Single-Group, Pretest-Posttest.

E. Sample size, statistical methods, and power calculation

1. We will calculate point estimates and confidence intervals for all endpoints of interest and will use effect sizes estimated from this data to guide power analyses for future trials. We expect a positive change in MVPA, and in 1 measure of physical function. Continuation to a larger trial will be based on a positive response in at least one of these endpoints.
2. N=20. The sample size was determined from the number of subjects that could feasible be recruited in the 1-year timeline for the grant and within the grant budget.

F. Subject Criteria (See Vulnerable Populations appendix, if applicable): Primary care physician (PCP) clearance will be required for all participants. A form with PCP clearance will need to be signed before participation will be allowed. Inclusion criteria: 1) Young adults (18-30 yrs.) 2) Diagnosis of DS as determined by a Community Service Provider operating in our recruitment area under the auspices of a Community Developmental Disability Organization (CDDO). 3) Sufficient functional ability to understand directions, communicate preferences, wants, and needs through spoken language. 4) Living at home with a parent/guardian or in a supported living environment with a parent/caregiver who agrees to serve as a study partner. Exclusion criteria: 1) Unable to participate in MVPA. 2) Serious medical risk, e.g., cancer, recent heart attack, stroke, angioplasty as determined by their primary care provider (PCP).

1. Inclusion criteria: 1) Young adults (18-30 yrs.) 2) Diagnosis of DS as determined by a Community Service Provider operating in our recruitment area under the auspices of a

- Community Developmental Disability Organization (CDDO). 3) Sufficient functional ability to understand directions, communicate preferences, wants, and needs through spoken language. 4) Living at home with a parent/guardian or in a supported living environment with a parent/caregiver who agrees to serve as a study partner.
2. Exclusion criteria: 1) Unable to participate in MVPA. 2) Serious medical risk, e.g., cancer, recent heart attack, stroke, angioplasty as determined by their primary care provider (PCP)
 3. Withdrawal/Termination criteria: If at anytime during the intervention, the participant becomes unable to participate in exercise sessions, participation will be terminated by the investigator. If the participant asks to be withdrawn from the study, the participant will be removed.
 4. A study subject can participate in another study while participating in this research study.

E. Specific methods and techniques used throughout the study

1. Laboratory tests: Physical function will be assessed using the 6-minute walk test¹⁶, Timed Up and Go test¹⁷, and the Y-Balance Test¹⁸.
2. Leg strength will be assessed using a standard 5-repetition maximum protocol¹⁹ on a Cybex plate-loaded leg press. Hand grip strength of both the dominant and non-dominant hands will be assessed with a Jamar handgrip dynamometer (JWL Instruments, Chicago, IL)²⁰.
3. **Daily physical activity, specifically MVPA, will be assessed using a Fitbit that will be synced to a tablet computer (iPad). Daily physical activity across the 12-week study activity will be assessed using a Fitbit Versa 3 monitor worn on the non-dominant wrist during each day of the intervention. Real-time data from the Fitbit will be transferred via Fitbit's Open API using R, thus participant burden is minimal. Immediate participant feedback via a graphic display of daily steps, minutes of sedentary time, time spent in light, moderate and vigorous PA will be available on the iPad. This data, accessible to health educators, will be used to provide motivation and feedback during the virtual coaching sessions. Participants will be reminded to wear and charge the Fitbit during the individual support/education sessions and will receive automatic reminder messages via the iPad.**

Study Procedures: 6-minute walk test (6-minutes), Timed Up and Go test (5-minutes), and the Y-Balance Test (5-minutes). Leg strength will be assessed using a standard 5-repetition maximum protocol (5-minutes) on a Cybex plate-loaded leg press. Hand grip strength of both the dominant and non-dominant hands will be assessed with a Jamar handgrip dynamometer (JWL Instruments, Chicago, IL), (5-minutes). Physical activity enjoyment will be assessed using the Physical Activity Enjoyment Scale (10-minutes). Self-efficacy will be assessed using the Self-Efficacy for Activity for Persons with Intellectual Disabilities Scale (10-minutes). Energy expenditure of a ring-fit session will be assessed in a volunteer sample of both patient and caregiver using a previously validated portable, open-circuit indirect calorimeter (Cosmed, Italy) which measures breath-by-breath ventilation, expired oxygen, and carbon dioxide. Study staff will schedule the assessment with participants which will involve a visit to the lab. The flow turbine will be calibrated using a 3.0-L syringe. The lightweight (~1.5 kg) portable system will be attached by a harness around the waist and shoulders of the participant

before each assessment. The device will be programmed utilizing study ID numbers, with no other identifying information. During exercise sessions, participants will breathe into a facemask that directs air into the unit housing the O2 and CO2 analyzers. Data will be retrieved for analysis via a serial port interface and downloaded to a university monitored, HIPPA compliant computer once staff returns to campus. Software provided with the calorimeter will be used to analyze data by aggregating over 20-second epochs for the calculation of 1-min averages. MET levels will be age corrected using the Schofield equation²¹ as recommended by McMurray et al²². Participants will be asked to wear both hip and wrist ActiGraphs during the assessment for comparison of physical activity levels between devices.

4. Timeline:

Timepoint	Action	Duration/Delivery
Week 0	Pre-Testing. 6-minute walk test, Timed Up and Go test, Y-Balance Test. 5-repetition maximum Leg Press, Hand grip strength (both hands). Physical Activity Enjoyment Scale, Self-Efficacy for Activity for Persons with Intellectual Disabilities Scale. RF Set-up Fitbit/iPad Set-Up	120 minutes. Kirmayer Fitness Center
Week 1	Intervention (RF sessions + virtual health coaching session)	90 minutes At home RF sessions, virtual health coaching on zoom.
Week 2	Intervention (RF sessions + virtual health coaching session)	120 minutes At home RF sessions, virtual health coaching on zoom.
Week 3	Intervention (RF sessions + virtual health coaching session)	150 minutes At home RF sessions, virtual health coaching on zoom.
Weeks 4-12	Intervention (RF sessions + virtual health coaching session)	180 minutes At home RF sessions, virtual health coaching on zoom.
Week 13	Post-Testing 6-minute walk test, Timed Up and Go test, Y-Balance Test. 5-repetition maximum Leg Press, Hand grip strength (both hands). Physical Activity Enjoyment Scale, Self-Efficacy for Activity for Persons with Intellectual Disabilities Scale.	120 minutes. Kirmayer Fitness Center

	Qualitative Interview	
	Energy Expenditure Test (Cosmed)	

Time frame for completion: Months 1-5: Recruit participants, complete the 12-week pilot trial of GameSquadDS, and conduct post intervention semi-structured interviews. Month 6: Complete data analysis for all process and physical outcomes.

F. Risk/benefit assessment:

1. Physical risk- "You might have muscle soreness, fatigue, nausea, dizziness. There is a very rare chance of unpredictable changes in blood pressure or heart rhythm, and heart attack."
2. Psychological risk- "You might feel uncomfortable answering some of the questions in the questionnaire."
3. Social risk- N/A
4. Economic risk- N/A
5. Potential benefit of participating in the study
 - a. Being in this study could help you find another method of exercise you enjoy. This may prove useful for future exercise behavior after acquiring Ring-Fit Adventure™ and a Nintendo Switch™ at the conclusion of participation.
 - b. The researchers might learn more about how to get adults with Down syndrome to exercise.
 - c. There is currently considerable interest in increasing physical activity in adults with disabilities. This may prove beneficial to that effort.

G. Location where study will be performed: Kirmayer Fitness Center

H. Personnel who will conduct the study, including:

1. Indicate, by title, who will be present during study procedure(s): [name], [name], [name]
2. Primary responsibility for the following activities, for example:
 - a. Determining eligibility: [name]
 - b. Obtaining informed consent: [name]
 - c. Providing on-going information to the study sponsor and the IRB: [name]
 - d. Maintaining participant's research records: [name]
 - e. Completing physical examination: [name]
 - f. Taking vital signs, height, weight: [name]
 - g. Performing / conducting tests, procedures, interventions, questionnaires: [name]
 - h. Completing study data forms: [name]
 - i. Managing study database: [name]

I. Assessment of Subject Safety and Development of a Data and Safety Monitoring Plan

1. Elements of the plan include:
 - a. Persons/groups who will review the data (study team; independent safety monitor, data monitoring committee or formal DSMB): Study Team
 - b. Data/events that will be reviewed: Subject accrual (adherence to protocol regarding demographics, inclusion/exclusion) and Adverse Event Rates
 - c. Frequency of review: Monthly
 - d. Types of analyses to be performed: Means
 - e. Safety-related triggers that would cause the PI to stop or alter the study: The most likely scenario indicating the need to stop the investigation would be a failure to recruit or deliver the intervention as planned. Another issue relating to stopping rules for this trial would be new information. It is unlikely that any new information will become available during this trial that would necessitate stopping the trial
2. Data on adverse events will be reported monthly to the PI throughout this trial. We anticipate that most adverse events will be mild in nature and will allow a complete return to the same activities after a short period of time; that is, later that day or a day or two later.
3. We anticipate most adverse events (if not all) will allow a complete return to the same activities after a short period of time; that is, later that day or a day or two later. However, if a serious adverse event that prohibits participation moving forward, the participant will be terminated from the intervention.

III. Subject Participation

A. Recruitment:

1. The recruitment plan was informed by our experience with completed projects where we successfully recruited adults with DS (DK083539, HD094704, AG036909). As in our previous trials, project staff will contact local community agencies serving adults with DS, case managers, and CDDOs by mail or email, provide presentations at CDDO meetings, and text for CDDO newsletters describing the project. Interested adults with DS or their parent/caregiver will be asked to contact the study coordinator via email, our website, or a dedicated toll-free study phone number that will be included in all recruitment materials. The study coordinator will contact interested individuals by phone to answer questions and conduct an initial eligibility screen. Zoom® meetings will be scheduled with those remaining interested and potentially eligible to complete eligibility screening and to obtain informed consent or parent/guardian consent and participant assent in cases where the participant has a surrogate decision maker. We will attempt to recruit ~50% female and ≥ 30% minorities. Study staff will forward a form to the PCP requesting permission to participate.

Screening Interview/questionnaire: Screening for potential study participants will be done using an interest and enrollment questionnaire (IEQ). The IEQ will have relevant qualification criteria based on the inclusion criteria for the pilot study. It will also have contact information for potential study participants to allow the principal investigator or study coordinator to reach the parent, legal guardian, or caregiver of the adult with DS. A

REDCap link to the IEQ will be distributed on the flyer and data will be stored in the secure, HIPAA-compliant database. Potential participants who meet the eligibility criteria for the research study will be contacted to review the study and the informed consent.

Questions for the questionnaire include:

- Do you have Primary Care Physician clearance to participate?
- Are you between 18-30 years old?
- Have you been diagnosed with DS?
- Do you have the ability to understand directions, communicate preferences, wants, and needs through spoken language?
- Are you living at home with a parent/guardian or in a supported living environment with a parent/caregiver who agrees to serve as a study partner?
- Are you able to participate in moderate to vigorous exercise?
- Do you have a serious medical risk (e.g., cancer, recent heart attack, stroke, angioplasty)?

The study coordinator will contact interested individuals by phone to answer questions and conduct an initial eligibility screen. Zoom® meetings will be scheduled with those remaining interested and potentially eligible to complete eligibility screening and to obtain informed consent or parent/guardian consent and participant assent, via Redcap, in cases where the participant has a surrogate decision maker

B. Informed consent process and timing of obtaining of consent

- 1 [name] will obtain written informed consent.
- 2 Remote video chat sessions (Zoom) will be scheduled with participants and their legal guardian (if they are not their own guardian) who are deemed to be initially eligible to participate. This video chat session will provide an opportunity to describe the project in detail, answer questions, verify eligibility, and to obtain consent and assent. Prior to the consenting session, the participant will be sent the consent form and cover letter through The University of Kansas Medical Center's (KUMC) secure email system. The study team will use the "share screen" option on Zoom to walk through each section of the consent document while noting questions that arise and answering these questions fully. Participants who are willing to participate in the study will sign and date the consent and/or assent forms electronically via REDCap. Participants/caregivers will be given unlimited time to make the decision on whether to participate. The study team member who conducted the consent meeting will also sign and date after reviewing the signed consent forms and verifying completeness. Study staff will provide the participant with a fully signed consent form for their records. Medical consent from the participant's physician will also be obtained prior to enrollment in the study. The physician will receive a description of the study and a request for medical clearance to participate in the physical activity
- 3 Subjects whom are not their own legal guardian will require a caregiver to give consent. [name] will make the determination.

C. Alternatives to Participation: The Alternative to participation would be not enroll in the study.

- D. Costs to Subjects:** There will be no cost to the subject for any testing or participation related to this study.
- E. How new information will be conveyed to the study subject and how it will be documented:** It is unlikely that new information would be presented during this study, however, the study team would review new information and take action accordingly.
- F. Payment, including a prorated plan for payment:** Participants will be provided with Fitbit, Ring-Fit Adventure™ and the Nintendo Switch™ gaming system if eligible and after completing the pre-testing appointment. Participants will need to complete the intervention to keep the Fitbit, Ring-Fit Adventure™, and the Nintendo Switch™. Travel costs will not be reimbursed.
- G. Payment for a research-related injury:** Participants will not be paid for a research-related injury.

IV. Data Collection and Protection

A. Data Management and Security:

1. Data will be entered into separate tables via the web using SSL encryption, and stored in a secure SQL database, housed behind a HIPAA compliant firewall. Database access will be limited to primary investigators and study coordinator. Data will be linked by participant ID. Identifiable information and outcome data will be stored separately. Only de-identified data will be available to study personnel. Research assistants, blinded to intervention assignment, will complete all data entry. All personnel have current Human Subjects/HIPAA certificates. [name], [name], and [name] will have access to the data.
2. Data will be entered into separate tables via the web using SSL encryption, and stored in a secure SQL database, housed behind a HIPAA compliant firewall. Database access will be limited to primary investigators and study coordinator. Data will be linked by participant ID. Identifiable information and outcome data will be stored separately. Only de-identified data will available to study personnel. Research assistants, blinded to this intervention will complete all data entry. All personnel have current Human Subjects/HIPAA certificates.
3. Participant IDs will be utilized.
4. [name] will have access to the code.
5. Data will be linked by participant ID. Identifiable information and outcome data will be stored separately.
6. Data will be entered into separate tables via the web using SSL encryption, and stored in a secure SQL database, housed behind a HIPAA compliant firewall. Database access will be limited to primary investigators and study coordinator. Data will be linked by participant ID. Identifiable information and outcome data will be stored separately. Only de-identified data will available to study personnel. Research assistants, blinded to this intervention will complete all data entry. All personnel have current Human Subjects/HIPAA certificates.

- B. Procedures to protect subject confidentiality:** Data will be entered into separate tables via the web using SSL encryption, and stored in a secure SQL database, housed behind a HIPAA compliant firewall. Database access will be limited to primary investigators and study

coordinator. Data will be linked by participant ID. Identifiable information and outcome data will be stored separately. Only de-identified data will be available to study personnel.

C. Quality Assurance / Monitoring

1. Research personnel will be observed by co-investigators for their first three sessions. Feedback will be given to ensure future sessions go as planned.
2. There are no plans to have third-party monitoring.

V. Data Analysis and Reporting

A. Statistical and Data Analysis: We will calculate point estimates and confidence intervals for all endpoints of interest and will use effect sizes estimated from this data to guide power analyses for future trials. We expect a positive change in MVPA, and in 1 of the measures of physical function. Continuation to a larger trial will be based on a positive response in at least one of these endpoints.

Thematic analysis will be used to analyze qualitative data completed by research personnel²³.

B. Outcome: We expect a positive change in MVPA, and in 1 of the measures of physical function. Continuation to a larger trial will be based on a positive response in at least one of these endpoints.

C. Study results to participants: All results will be given to the subjects after completion of the post-testing appointment. An interview will be given going over the results and giving the participants a hand-out of all outcomes. This is due to the potential of positive results after being physically active, and could have ramifications on future behavior.

D. Publication Plan: Publication will be sought as a pilot, feasibility study based on quantitative and qualitative results from all outcomes.

Bibliography / References / Literature Cited

2. Changes in cognitive function after a 12-week exercise intervention in adults with Down syndrome.

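### No pre-intervention MVPA measurement is described in a pretest-posttest plan, and the continuation rule leaves both its criterion and its function test open

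*Combined protocol and SAP*

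**What the plan says.** Section II.D gives the design as "Study Type and Design: Single-Group, Pretest-Posttest". Section II.B makes the effect size for MVPA change across 12 weeks a secondary aim.

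On analysis, II.E.1 (sample size, statistical methods) says: "We will calculate point estimates and confidence intervals for all endpoints of interest", and that the team "will use effect sizes estimated from this data to guide power analyses for future trials". It then says "We expect a positive change in MVPA, and in 1 measure of physical function", and: "Continuation to a larger trial will be based on a positive response in at least one of these endpoints". Sections V.A and V.B repeat the expectation and the rule with nothing material added.

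On measurement, the section on specific methods and techniques lists three function tests. It begins "Physical function will be assessed using the 6-minute walk test" and goes on to the Timed Up and Go and the Y-Balance Test. MVPA comes from a "Fitbit Versa 3 monitor worn on the non-dominant wrist during each day of the intervention". During that wear the participant receives "Immediate participant feedback via a graphic display of daily steps" and activity minutes, which health educators also use in coaching.

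The Timeline table lists Fitbit and iPad set-up at Week 0. Neither the Week 0 nor the Week 13 test list contains an MVPA measurement. Section III.F (Payment) says the Fitbit is provided after the pre-testing appointment. ActiGraphs are mentioned only for the energy-expenditure session.

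**The concern.** **MVPA reference.** A pre-post change needs a value from before the intervention. On the plan as written, the earliest MVPA data that anyone is told to collect come from week 1, when play, coaching and live feedback have already started. No end window is stated either. MVPA change is a secondary-aim effect size, an input to the power analysis of the next trial, and one of the two routes to continuation. A reference that already carries part of the effect compromises all three uses.

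**Continuation rule.** The rule has no threshold, no minimum change, no link to the planned confidence intervals, no confidence level and no stated direction. Direction matters because improvement on the Timed Up and Go is a shorter time. The function endpoint is one unnamed test out of three. Both the criterion and the test could therefore be chosen after the results are known, and the loosest reading hardly separates an effective intervention from an inert one.

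**Working it through.** N=20 is justified by recruitment and budget, with no power claim, so there is no stated calculation to reproduce.

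**1. Where MVPA is measured**

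| Place | What it provides |
|---|---|
| II.D, II.B | Pre-post design; MVPA change across 12 weeks |
| III.F | Fitbit supplied after pre-testing |
| Timeline, Week 0 | Fitbit/iPad set-up only |
| Methods, daily physical activity | Wear on each day of the intervention, with feedback |
| Timeline, Week 13 | No MVPA in the post-test list |

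An early-to-late contrast can be computed, but week 1 is its earliest described reference.

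**2. What a week-1 reference could do to the effect size**

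Inputs from the Timeline: 90 minutes in week 1 and 180 in weeks 4–12. Both figures are attached to game sessions plus coaching, and the documents do not split them. Assumptions: MVPA gain is proportional to game minutes, the SD is the same, and a constant c minutes per week is coaching.

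Share of the effect kept = 1 − (90 − c)/(180 − c). Required sample size scales as 1/share².

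| c | Game minutes, week 1 / full | Share kept | Sample-size factor |
|---|---|---|---|
| 0 | 90 / 180 | 0.50 | 1/0.50² = 4.0 |
| 30 | 60 / 150 | 0.60 | 1/0.60² = 2.8 |
| 60 | 30 / 120 | 0.75 | 1/0.75² = 1.8 |

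For illustration, take a true 0.5 SD in a two-arm trial with 80% power and two-sided 5%. Then n per arm = 2 × ((1.960 + 0.842)/d)². This gives 63 at d = 0.5, 252 at 0.25 (c = 0), 175 at 0.30 (c = 30) and 112 at 0.375 (c = 60).

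**3. The continuation rule if any favourable mean change counts**

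Assumptions: normal changes with equal correlation ρ between endpoints. With no true change each mean is favourable with probability 0.5, whatever n is. For k endpoints, P(go) = 1 − P(all k unfavourable). This is 1 − 0.5^k at ρ = 0 and 1 − 1/(k + 1) at ρ = 0.5; ρ = 0.8 was obtained numerically.

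| Endpoints that can trigger go | ρ = 0 | ρ = 0.5 | ρ = 0.8 |
|---|---|---|---|
| MVPA or any of three tests (k = 4) | 94% | 80% | 69% |
| Three function tests alone (k = 3) | 88% | 75% | 65% |
| MVPA or one pre-named test (k = 2) | 75% | 67% | 60% |

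The k = 4 and k = 2 rows treat MVPA as having a genuine pre-post value, which part 1 shows is not described. The k = 3 row does not need it. With a true 0.5 SD change in every endpoint and n = 20, P(go) is at least 99.5% in every cell, so for k = 4 go is only 1.07 to 1.45 times as likely as with no change.

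**4. An example of a defined rule**

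Either of two named endpoints, lower limit of a two-sided 80% CI above zero, n = 20, paired t, simulated with ρ from 0.8 to 0:
- no true change: go 14–19% (at ρ = 0, 1 − 0.9² = 19%)
- true 0.3 SD in both: go 62–76%, so no-go 24–38%
- true 0.5 SD in both: go 89–97%

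**The case against.** This is a feasibility pilot with estimation as its stated analysis, and an N set by budget is acceptable. That stands: nothing here asks for power or a larger N. It does not answer the point, because the plan sets its own continuation rule and that rule cannot be applied as written.

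Several stronger readings are tempting, and the documents do not support them.

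- **That the MVPA baseline is irrecoverably lost.** The device is set up at Week 0 and its data transfer in real time, so some days before the first session may be recorded. What can be said is that no such measurement is specified.
- **That a later trial would need four times the patients.** This treats 90 and 180 minutes as pure game time. The table attaches them to play plus coaching, so a factor of 4 is the zero-coaching end of a range.
- **That the wording spans false-go rates from about 4% to 94%.** The low end comes from a 95% CI reading at correlation 0.8 and the high end from a sign reading at correlation 0. Both count an MVPA baseline that is not described. Part of that width comes from the assumptions rather than the text.
- **That drift or practice effects inflate the go rate.** The documents give no data on direction. Section I.B describes functional decline in this population, and novelty or device wear could fade. Either direction is possible.
- **That a CI excluding zero is the only acceptable criterion.** At n = 20 such a rule misses real effects fairly often. Choosing it over a minimum change is a trade-off.

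**Conclusion.** Both parts hold, and the missing MVPA reference is the main one. It rests on the text alone: followed as written, the plan yields no untreated MVPA value for an effect size meant to inform later power analyses. The direction of the resulting error (understatement) depends on the intervention raising MVPA from the start. Its size, 50–75% of the effect kept and a later trial 4 to 1.8 times too large, depends on proportional gain, equal SD and 0 to 60 coaching minutes per week, none of which the documents give.

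The undefined rule is also a fact of the text. Under its loosest reading, continuation with no true change is likely in every variant examined: 60–94% across the three endpoint sets, and 67–80% at correlation 0.5. The correlations are assumed. The primary feasibility outcomes are not affected. This should be fixed before data are seen.

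**What to change.** 1. **MVPA windows** (methods section and Timeline). Add a short Fitbit wear period between Week 0 set-up and the first game session as the baseline, with the activity display off if feasible. State a matching end window, for example the last intervention week or weeks, and a valid-wear rule. If this is not possible, label the week-1 comparison as on-intervention and do not call it a pre-post change.
2. **Decision endpoints** (II.E.1, V.A, V.B). Before data are seen, name MVPA and one function test. State the favourable direction for each (shorter time if Timed Up and Go is chosen), and keep the other tests descriptive.
3. **Criterion.** Replace positive response with either a minimum change or a limit of the planned CI. Leave the choice and level to the sponsor, and state the false-go and false no-go rates. The 80% CI rule in the working is one example.
4. **Limitation.** State that a single-arm change cannot separate drift or practice effects from the intervention.

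The cost is wording in three places, a few sentences on the windows, and a few days' delay before the first session with a device already issued. Participants may react to wearing the device even with the display off. A defined criterion is stricter: the 80% CI example says no-go in 24–38% of trials when the true change is 0.3 SD in both endpoints.
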